6.6 Assessments

6.6.1 Assessments Overview

Behavioral assessments will be conducted at baseline and follow-ups. Follow-up assessments will be conducted at 1-, 2- (for those randomized to the DD condition only), 3-, 6-, and 9-months post-randomization to measure methamphetamine use, HIV sexual risk behaviors, and advancement along the HIV Prevention or Care Continuum.

6.6.2 Behavioral Assessments

6.6.2.1 DSM-5 Methamphetamine Use Disorder contains the DSM-5 diagnostic items necessary to make a determination of mild, moderate, or severe methamphetamine use disorder. This information will determine the app's utility for consumers at various levels of methamphetamine use. DSM-5 diagnostic criteria for other substance use disorders will also be collected. Administered at baseline only.

6.6.2.2 University of Rhode Island Change Assessment (URICA) is a brief, self-administered inventory used to assess the participant's current position regarding readiness for change (e.g., precontemplation, contemplation, action). Administered at all time points.

6.6.2.3 Admission/Follow-up Form collects demographic information, housing status, food security, educational attainment, alcohol and other drug use history, family and social history, legal status, HIV status, location on the HIV Prevention or Care Continuum, experiences with stigma and/or discrimination, and general and mental health status. The full form will be administered at baseline, an abbreviated version at all follow-up time points.

6.6.2.4 Substance Use Frequency is a brief assessment, developed by [name] (Principal Investigator) that assesses substance use, injection drug use, and injection protocols in the past 30 days. Administered at all time points.

6.6.2.5 Behavioral Questionnaire – Amphetamine (BQA)-Abbreviated Version gathers information on HIV-related drug and sexual risk behaviors, assesses self-efficacy for sexual behavior change, and collects detailed information on discrete sexual behaviors (with primary or non-primary partners and whether or not the behavior occurred under the influence of methamphetamine and/or other substances), as well as episodic data about participants' most recent sexual encounters. Administered at baseline, and an abbreviated version is administered at all follow-up time points.

6.6.2.6 PrEP Uptake and Adherence is a brief assessment, developed by [name] (Principal Investigator), that gathers information of PrEP readiness, initiation and adherence to access advancement along the HIV Prevention Continuum. Administered at all time points.

6.6.2.7 ART/HIV Care is a brief assessment, developed by [name] (Principal Investigator), that gathers information of HIV care and ART medication adherence to access advancement along the HIV Care Continuum. Administered at all time points.

6.6.3. Biomarker Assessments

6.6.3.1 HIV-antibody Test. HIV-negative and status unknown participants will receive a fingerstick DBS test at 3-month intervals, as recommended by the CDC for high-risk individuals. Participants who show documentation of HIV-positive serostatus are not given a HIV-antibody test. If the test is reactive, then the participant will be presumed positive for HIV antibodies and referred for additional evaluation and treatment. If the DBS sample is rejected by the lab or if the quantity of blood is insufficient, participants will be asked to come to the study site to have the test performed via fingerstick blood test using the INSTI HIV 1/HIV 2 antibody test, or to provide a copy of recent results (within 3 months) from their medical provider. Conducted at baseline and at the 3-, 6-, and 9-month follow-up time points (if previously tested HIV-negative or status is unknown).

6.6.3.2 STI Testing. Participants will be tested for urinary N. gonorrhoea and Chlamydia, pharyngeal and rectal swabs will be taken for N. gonorrhoea and Chlamydia, and syphilis will be tested by fingerstick DBS. Positive STI results will be reported per state guidelines and will be immediately referred to care. If the DBS sample is rejected by the lab or if the quantity of blood is insufficient, participants will be asked to come to the study site to have the test performed via intravenous blood draw or to provide a copy of recent results (within 3 months) from their medical provider. Conducted at baseline and at the 3-, 6-, and 9-month follow-up time points.

6.6.3.3 Virologic Control for HIV-positive Participants. As indicated by an undetectable HIV-1 level via intravenous blood draw, which has a threshold for undetectability = <30 copies/mL will be performed by Foundation Laboratory. Viral load testing through Foundation Laboratory may be bypassed if participants can provide recent (within 3 months) lab results from their medical provider. Conducted at baseline and at the 3-, 6-, and 9-month follow-up time points.

6.6.3.4 Dried Blood Spot (DBS) for HIV-negative Participants who Report PrEP Uptake. A blood sample will be collected and a DBS analysis for intra-erythrocytic TFV-DP will be performed by Molecular Testing Labs. Conducted at baseline and at the 3-, 6-, and 9-month follow-up time points.

6.6.4. Follow-up Locator Questionnaire

6.6.4.1. Health Study Locator Questionnaire. The locator form was originally developed by UCLA Integrated Substance Abuse Programs (ISAP) investigators for the Methamphetamine Treatment Project to facilitate contact with the participant during intervention and follow-up and has been modified by the Principal Investigators for MSM. The form asks participants to give consent for follow-up and to provide names, addresses, email and Internet site profiles, particularly social network sites, and phone numbers of relatives and friends who can reach the participant in emergencies. Information is also collected on where (libraries, clubs, bars) and with whom the participant associates (i.e., social network), and a physical description, including tattoos, scars, and birthmarks.

7.0 **TIMELINE**

The timeline and research procedures are presented in Table 1.

Table 1. Timeline and Activities

Timeline of Research Procedures		Aim	Year 1 7/15/18-4/30/19				Year 2 5/1/19-4/30/20				Year 3 5/1/20-4/30/21				Year 4 5/1/21-4/30/22				Year 5 5/1/22-4/30/23			
Month:			Aug, Sep, Oct	Nov, Dec, Jan	Feb, Mar, Apr	May, Jun, Jul	Aug, Sep, Oct	Nov, Dec, Jan	Feb, Mar, Apr	May, Jun, Jul	Aug, Sep, Oct	Nov, Dec, Jan	Feb, Mar, Apr	May, Jun, Jul	Aug, Sep, Oct	Nov, Dec, Jan	Feb, Mar, Apr	May, Jun, Jul	Aug, Sep, Oct	Nov, Dec, Jan	Feb, Mar, Apr	
Milestones:		N/A																				
Develop study materials & protocol	n/a		X																			
Obtain IRB/regulatory approval	n/a		X																			
Obtain CoC	n/a		X																			
The Formative Stage																						
Convene Community Advisory Board	1 & 2			X		X		X		X		X		X		X		X		X		
Conduct focus groups	2			X																		
App development (sessions 1-24)	1 & 2				X	X	X	X	X	X	X	X										
Alpha phase (post-development bug testing)	2												X									
Beta phase (usability pilot study)	2													X								
App refinement	2													X								
Hire and train Research Assistant	n/a														X							
The RCT Stage																						
Recruit & enroll ~25-30 participants/mo (N=300)	3														X	X	X	X	X			
1-, 2-, 3-, 6-, 9-month f/u assessments	3														X	X	X	X	X	X	X	
Data cleaning & analysis	3														X	X	X	X	X	X	X	
Report and manuscript preparation	n/a																			X	X	
Dissemination of findings	n/a																		X	X	X	

8.0 STATISTICAL ANALYSES

8.1 General Analytical Approach

All primary outcomes are operationalized and assessed in at least two discrete ways, increasing accuracy of measurements, reducing concerns of fully missing data, and allowing for post-hoc comparisons of concurrent validity across assessment modalities (see Table 2 for all outcome operationalizations). Descriptive statistics will be calculated and provided for all outcomes, with specific metrics chosen based on the distributional properties of each variable (e.g., counts and percentages for nominal variables; means and standard deviations for parametric continuous variables; ranges and medians for non-parametric continuous variables). Diagnostic (i.e., DSM-5), psychosocial (e.g., URICA), barriers and facilitators (e.g., housing insecurity, lack of transportation), and/or sociodemographic variables will be tested for significant association with study outcomes (i.e., advancement through the HIV Prevention or Care Continuum, methamphetamine use, HIV sexual risk behaviors), with specific tests of association chosen based on the distributional properties of the outcome variables in question. All variables demonstrating significant statistical association with one or more of the study outcomes will be included as statistical covariates in all multivariate outcome analyses associated with Specific Aims 1a-1c, and will additionally be included in exploratory sub-group analyses to test for moderating effects on treatment response and/or contingent effects among subsets of participants. Primary outcome analyses for Specific Aims 1a, 1b, and 1c will be carried out using mixed effects Generalized Linear Model (GLM) equations.

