2.0 INTRODUCTION

2.1 Rationale

Methamphetamine use among MSM is associated with increased rates of HIV prevalence and transmission, as well as substandard advancement along the HIV Prevention and Care Continua. Methamphetamine use among MSM is deeply integrated into socio-sexual networks including the use of smartphone apps and websites to find sexual partners. Given the growth of mobile health technology, it is no longer necessary or reasonable to limit methamphetamine treatment options to physical sites, clustered in urban areas, and administered using generic, non-tailored content. The project builds upon the established efficacy of our manualized methamphetamine-use treatment intervention, “*Getting Off: A Behavioral Treatment Intervention for Gay and Bisexual Male Methamphetamine Users*,” and the highly promising findings from the successful Stage I proof-of-concept study, to complete translation of *Getting Off* into a cross-platform (iOS and Android) app and assess the app’s efficacy *and* non-inferiority in a scientifically rigorous randomized trial. The *Getting Off* app, like the group-based intervention before it, will use the principles of Cognitive Behavioral Theory and Stages of Change to help MSM reduce or eliminate methamphetamine use and HIV sexual risk behaviors, and increase advancement along the HIV Prevention or Care Continuum (including uptake of HIV testing, pre-, and post-exposure prophylaxis [PEP/PrEP] and PrEP adherence and persistence for those who are HIV negative; ART uptake and adherence for those who are HIV positive).

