6.4 Random Assignment

Following informed consent and completion of the baseline assessment, participants will be randomized to either the ID or DD arm through a computerized variable-balanced block randomization procedure. Recent work with MSM with substance use disorder (predominantly methamphetamine) at FCC revealed treatment outcomes to be associated with participant substance use histories and sociodemographics. A variable-balanced procedure will thus provide multivariate balance among the characteristics known or expected to influence outcomes. The randomization procedure will balance across age (<34, ≥ 34), race/ethnicity (Caucasian/White, all other race/ethnicities), HIV serostatus (+, -), and SOC (contemplation/preparation, action/maintenance).

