9.0 ANALYTIC APPROACH

9.1 Specific Aim 1a Analysis

Aim 1a, which begins the efficacy trial, is a two-arm, non-blinded RCT whereby half of all participants are randomly assigned to receive the Getting Off app immediately (ID arm; n=150; equivalent to an “active intervention” arm) and half are randomly assigned to receive the app after a 30-day delay (DD arm; n=150; equivalent to a “control” arm). The proposed analytical model allows for causal analysis of intervention effects. Power Calculations for Specific Aim 1a: estimated RCT MDEs for HIV Prevention or Care Continuum outcomes related to Specific Aim 1a are: 1) dichotomous (Di)—Odds Ratio (OR) = 1.97; 2) counted (Cu)—Incidence Rate Ratio (IRR) = 1.51; 3) continuous (Co)— f^2 = 0.03; for methamphetamine use outcomes: 1) Di—OR = 0.48; 2) Cu—IRR = 0.85; 3) Co— f^2 = 0.05; for HIV sexual risk behaviors outcomes: 1) Di—OR = 0.52; 2) Cu—IRR = 0.78; 3) Co— f^2 = 0.05.

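### Section 8.1 selects covariates by significance against the trial's own outcomes and does not restrict them to baseline values, so values the app may change can enter the Aim 1a model

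*Combined protocol and SAP*

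**What the plan says.** Section 8.1 screens diagnostic, psychosocial (URICA is the example), barrier/facilitator and sociodemographic variables against the three study outcomes. It then states that "variables demonstrating significant statistical association with one or more of the study outcomes will be included as statistical covariates in all multivariate outcome analyses" for Specific Aims 1a to 1c. It gives neither a screening threshold nor a measurement time. Table 2 repeats the DSM-5, URICA and Admission/Follow-up Form variables as possible statistical controls.

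The candidates are measured at different times:

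- URICA (6.6.2.2) covers "readiness for change (e.g., precontemplation, contemplation, action). Administered at all time points".
- Admission/Follow-up Form (6.6.2.3), which includes housing, food security and stigma: "The full form will be administered at baseline, an abbreviated version at all follow-up time points".
- DSM-5 items (6.6.2.1): "DSM-5 diagnostic criteria for other substance use disorders will also be collected. Administered at baseline only".

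Section 2.1 says the app "will use the principles of Cognitive Behavioral Theory and Stages of Change to help MSM reduce or eliminate methamphetamine use". Section 6.4 names the randomisation factors ("The randomization procedure will balance across age", race/ethnicity, HIV serostatus and stage of change), but no section fixes them as model terms. Section 9.1 says of Aim 1a: "The proposed analytical model allows for causal analysis of intervention effects".

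**The concern.** A randomised comparison keeps its causal meaning when the adjustment variables could not have been affected by treatment. Section 8.1 does not secure that. Stage of change is something the app sets out to move, and URICA is collected again at month 1, the only follow-up visit before the delayed arm gets access. The primary models are mixed models for repeated measures, in which a visit-level URICA value is easy to enter and satisfies the rule as written. Conditioning on it can remove part of a real effect. It can also create an apparent effect where there is none, if readiness and use share causes outside the trial.

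A lesser issue is that the four factors used to balance the arms enter the model only if they happen to test significant.

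**Working it through.** **1. The plan's own figure.** Inputs: 150 per arm and OR 0.48 (9.1); 80% use in the delayed arm before access (8.2); two-sided 0.05 and power 0.80 (8.3). Treated odds are 4 × 0.48 = 1.92, so the treated proportion is 1.92/2.92 = 0.658. The pooled-variance two-proportion formula for 0.80 versus 0.658 gives power 0.796. The same method gives 0.796 for sexual risk (0.65, OR 0.52) and 0.807 for the continuum (0.30, OR 1.97). The stated effects therefore match an unadjusted two-arm comparison with complete data, and none of them is disputed here.

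**2. Baseline candidates only.** Simulation with 150 per arm, four binary factors balanced across 16 cells and three dichotomous outcomes; a factor enters if p < 0.05 on any outcome. Factor odds ratios are assumed.

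- At factor OR 1.25, 1.5 and 2.0, each factor enters in 37%, 72% and 97% of trials.
- Power for use under the rule is 80.5%, 80.3% and 82.8%, against 80.6%, 80.5% and 82.8% with all four forced in. Allowing for persistent differences between people, the gain from forcing them in is at most 0.4 points.
- Type I error under the rule is 4.3% to 5.4%. A separate linear-model check with 10 to 40 candidates gave 4.5% to 5.4%.
- Adding the baseline value of the outcome gains about 1 to 5 points at an assumed baseline correlation of 0.18 to 0.35, and only if the mixed model does not already use baseline.

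**3. Follow-up URICA admitted.** Let M = d·arm + Z, where d is the app's shift in SD units. Let the logit of use be a + θ·arm − b·Z, so Z is related to use but the shift itself is not. Substituting Z = M − d·arm gives a coefficient for arm, given M, of θ + b·d instead of θ. The bias is toward harm.

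Rough size at p = 0.80: b ≈ r/√(p(1−p)) = r/0.4. With ln 0.48 = −0.734 and a standardised effect of 1.96 + 0.84 = 2.80 at 80% power, power given M ≈ Φ(2.80 × (1 − b·d/0.734) − 1.96).

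- d = 0.2, r = 0.1: b·d = 0.25 × 0.2 = 0.05. Null OR e^0.05 = 1.05; power Φ(0.65) = 74%.
- d = 0.3, r = 0.2: b·d = 0.50 × 0.3 = 0.15. Null OR 1.16; power Φ(0.27) = 61%.
- d = 0.5, r = 0.3: b·d = 0.75 × 0.5 = 0.375. Null OR 1.45; power Φ(−0.59) = 28%.

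Simulation with the selection step included (M enters if p < 0.05) agrees:

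| r with use | Power at OR 0.48, d = 0.2 / 0.3 / 0.5 | Rejection with no effect, d = 0.2 / 0.3 / 0.5 |
|---|---|---|
| 0.1 | 75.9 / 72.0 / 64.6% | 4.3 / 4.2 / 4.9% |
| 0.2 | 68.4 / 61.5 / 45.2% | 6.5 / 7.7 / 11.9% |
| 0.3 | 64.0 / 54.2 / 29.7% | 8.1 / 12.0 / 26.3% |
| Without M | 78.4 to 80.3% | 4.1 to 5.0% |

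The median adjusted odds ratio with no true effect runs from 1.05 to 1.52.

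**4. If readiness really is the pathway.** Linear model, n = 300, total effect set for 80% power, covariate always included. If the month-1 covariate carries 25%, 50% or 75% of the effect (assumed), the adjusted estimate is about 75%, 50% or 25% of the total. Power is 58–67%, 30–36% or 10–12%.

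**The case against.** The strongest reply is that this rests on silence. Section 8.1 nowhere says follow-up values will be used, and the context leans toward baseline. The same sentence sends these variables into moderator analyses, where baseline values are usual. The DSM-5 items are baseline only, and stage of change is already a pre-randomisation factor. That stands as a reading of intent. It does not amount to a restriction: the protocol marks the DSM-5 items as baseline only where it means that, and the covariate rule carries no such limit.

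Second, d and r have no source in the documents, and the model in step 3 moves readiness without any consequence for use, contrary to the app's premise. This is fair. The figures show what could happen, not what is expected, and the mildest setting costs only about 3 to 4 points of power. Step 4 takes up the premise that readiness drives use, and the loss there is also substantial.

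Three stronger readings are tempting but unsupported:

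- A reader might infer that significance screening itself inflates type I error. Step 2 shows it does not when candidates are baseline values.
- A reader might infer that the plan has no usable month-1 outcome because the biomarkers in 6.6.3 resume at month 3. Section 8.1 refers to Table 2 for the outcome definitions. Table 2 lists self-report versions available at month 1 and attaches the Aim 1a detectable effects to those rows.
- A reader might infer that success on any one version of an outcome would be claimed. The plan states no such rule and gives other reasons for multiple versions: accuracy, missing data and concurrent validity.

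**Conclusion.** The point holds as a gap in the covariate rule. The rule permits post-randomisation values in a model the plan calls causal, and no section closes that gap. If follow-up URICA entered, power for methamphetamine use at OR 0.48 would fall from about 80% to between 76% and 30%, and the rejection rate with no effect would be about 4% to 26%. Both ranges assume shifts of 0.2 to 0.5 SD, correlations of 0.1 to 0.3 and complete data. If only baseline values are used, the selection rule does no measurable harm to error rates and costs almost no power, so fixing the balancing factors is good practice more than a rescue. No stated number is wrong. This is an improvement that costs nothing and should be made. Confidence is medium because the harm depends on how an ambiguous rule would be applied.

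**What to change.** 1. **Aim 1a.** Replace the selection rule with a fixed set measured at baseline: age, race/ethnicity, HIV status and stage of change as balanced in 6.4, plus the baseline value of the outcome (as a covariate or as a baseline response in the mixed model). State where precontemplation falls, since the two stage categories in 6.4 do not list it. Keep other variables for sensitivity or moderator analyses.
2. **Aims 1b and 1c.** Exclude covariates measured after the participant's intervention period began, and leave the rest as written. For the delayed arm in Aim 1b, the month-1 visit is the pre-intervention visit under the plan's own pairing.
3. **Minor clarification.** State that the Aim 1a contrast is at month 1. Label as primary the Table 2 self-report versions that already carry the Aim 1a detectable effects (use/non-use, condomless anal intercourse, continuum advancement), with biomarker versions supportive.

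The cost is SAP wording. The factors are already coded for randomisation, the questionnaires are already scheduled, and sample size, alpha and the stated detectable effects do not change. The one trade-off belongs to item 3: month-1 primaries rest on self-report in a non-blinded trial, which is why the biomarker results should still be reported.

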***Getting Off:* A Theory-based mHealth Intervention for Methamphetamine-using MSM**

Lay Title: *Getting Off App*

DESIGN

Getting Off App is a randomized controlled trial (RCT) to assess the impact of *Getting Off*, a culturally competent Cognitive Behavioral Therapy-based app for reducing methamphetamine use, HIV sexual risk behaviors, and increase advancement along the HIV Prevention or Care Continuum, with the desired outcome of significant reductions in methamphetamine use and HIV sexual risk behaviors as well as increased odds of advancement along the HIV Prevention or Care Continuum among men who have sex with men (MSM), aged 18-65, who report using methamphetamine within the past year.

Over the course of 30-days, participants are asked to complete 24 intervention sessions in the *Getting Off* app derived from an existing, manualized, group-based intervention with established efficacy.

The study will implement a two-arm RCT to determine intervention effects through comparison of participants who are given immediate access to the *Getting Off* app (Immediate Delivery [ID]) and participants who are given access to the *Getting Off* app after a delayed 30-day period (Delayed Delivery [DD]).

DURATION

30 days

SAMPLE SIZE

300 participants (n=150: Immediate Delivery / n=150: Delayed Delivery)

POPULATION

MSM who are between the ages of 18 and 65 years of age, who have used methamphetamine within the past 365 days, who have their own Android or iOS running smartphone with a current data plan, and who are able and willing to provide informed consent and comply with study requirements.

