1.2 Secondary Aim

- 1.2.1 Secondary Aim 1: Determine the impact of structural- (e.g., housing insecurity, food scarcity, educational attainment, access to healthcare) and individual-level (e.g., homophobia, stigma, and discrimination) factors as moderators of intervention outcomes.

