8.3 HIV Sexual Risk Behavior

HIV sexual risk behavior outcomes will be assessed at all time points throughout the study, and will be operationalized dichotomously (e.g., incident STI via biomarker testing), as a counted variable (e.g., number of days/times engaged in CAI in the past 30 days), and as a continuous variable (e.g., a HIV risk severity index generated from multiple factor-analyzed items). Power calculations for engagement in HIV sexual risk behaviors assume a 65% probability of engagement during the pre-intervention period for participants in the DD arm (equivalent to ~2:1 odds of engagement). Multivariable inferential analyses of dichotomous outcomes will take the form of GLMs employing the Bernoulli family and logit link function; counted outcomes will be analyzed with GLMs employing the Poisson-log or negative binomial link functions as distributional patterns dictate (note: if data evidence an over-representation of zeros or an overdispersion of variance, zero-inflated Poisson and/or negative binomial analyses may be substituted); continuous outcomes will be analyzed using GLMs employing the identity link and Gaussian family functions and assume a single covariate unless otherwise stated (note: iteratively reweighted, bootstrapped, or jack-knifed estimation procedures may be used in Gaussian models if sensitivity analyses indicate undue influence from outliers). Mixed effects GLM models are considered the best linear unbiased estimators for repeated measures data employing non-parametric and/or limited dependent variables. All power calculations are premised on tests of association across two time points (e.g., baseline with app completion; app completion with brick-and-mortar program completion), providing the most conservative estimate of minimum detectable effect (MDE) size estimations; all power calculations assume $\alpha \leq 0.05$ (two-tailed), and $1 - \beta = 0.80$.

Table 2: Instruments, Targets, Variable Operationalizations, and Minimum Detectable Effects

Table 2: Instruments, Targets, Variable Operationalizations, and Minimum Detectable Effects (1 - β = 0.80; α = 0.05, two-tailed)

Instrument	Target	Variable Operationalizations			Power-- Minimum Detectable Effects		
		Dichotomous (Di)	Count (Cu)	Continuous (Co)	Model 1— RCT (Aim 1a; n=150/n=150)	Model 2— Tx Effects (Aim 1b; N = 300)	Model 3— Matched Comparison (Aim 1c; N = 300/N ~ 600)

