DSM-5 (MA)	Diagnosis of MA Use Disorder	Presence/Absence of MA Use Disorder	# of Diagnostic Criteria Endorsed	N/A	Potential Statistical Controls; Exploratory Sub-Group Analyses		
URICA	Stage of Change/ Readiness for Change	Above/Below "Action" Stage	N/A	URICA Score(s)	Potential Statistical Controls; Exploratory Sub-Group Analyses		
Admissions & Follow-up Form	Sociodemographics; HIV Status and Tx History, Barriers & Facilitators	Sexual Identity; HIV Status; Linked/Unlinked; Housing Insecurity	Prior Drug Treatment Episodes; Symptomology	Age; Income	Potential Statistical Controls; HIV-Related Sub-Group Analyses; Barrier/Facilitator Moderator Analyses		
	HIV Prevention or Care Continuum ^a	HIV Test; PrEP Uptake; Advance along HIV Prevention or Care Continuum	Prevention or Care Continua Steps Completed	N/A	Di: OR = 1.97; Cu: IRR = 1.51; Co: f^2 = 0.03	Di: OR = 1.61; Cu: IRR = 1.35	Di: OR = 1.52; Cu: IRR = 1.30; Co: f^2 = 0.01
Biomarker Tests (UA, VL, DBS, HIV/STI)	MA Use, HIV Prevention/Care Continuum Outcomes, Sexual Risk Behavior	Incident STI /Incident HIV	Log reductions in HIV VL; DBS Analysis of PrEP	Treatment Effectiveness Score	Variable	Variable	Variable
Substance Use Freq.	MA Use	Use/Non-use	Days of Use	N/A	Di: OR = 0.48; Cu: IRR = 0.85; Co: f^2 = 0.03	Di: OR = 0.59; Cu: IRR = 0.89; Co: f^2 = 0.01	Di: OR = 0.62; Cu: IRR = 0.90; Co: f^2 = 0.01
BQA	HIV Sexual Risk Behavior	CAI ^b	# CAI ^b Episodes	HIV Sexual Risk Scale	Di: OR = 0.52; Cu: IRR = 0.78; Co: f^2 = 0.03	Di: OR = 0.63; Cu: IRR = 0.85; Co: f^2 = 0.01	Di: OR = 0.66; Cu: IRR = 0.87; Co: f^2 = 0.01
Locator	Contact Information						

^aHIV Prevention Continuum (HIV testing and PrEP/PEP uptake) and HIV Care Continuum (link, ART adherence, virological suppression).

^bCAI: Condomless Anal Intercourse includes both receptive and insertive anal intercourse, and will be assessed by partner type (e.g., main, casual, exchange)

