9.2 Specific Aim 1b Analysis

Aim 1b completes the efficacy trial by doubling the size of the analytical sample and allowing for highly accurate specification of observed treatment effects; it is a single-arm, pooled (i.e., ID+DD) observed treatment effects analysis whereby data points from the ID arm are paired with their analytical comparators from the DD arm (i.e., ID enrollment data with DD 1-month post-enrollment data; ID 1-month post-enrollment data with DD 2-months post-enrollment data);

the proposed analytical model provides increased analytical power for HIV subgroup and/or contingency analyses, given the greater number of persons receiving the intervention relative to the proposed RCT model (i.e., N=300 receiving the app). Power Calculations for Specific Aim 1b: estimated pre-/post-test observed treatment effect MDEs for HIV Prevention or Care Continuum outcomes related to Specific Aim 3b are: 1) Di—OR = 1.61; 2) Cu—IRR= 1.35; for methamphetamine use outcomes: 1) Di—OR = 0.59; 2) Cu—IRR = 0.89; 3) Co—f2 = 0.01; for HIV sexual risk outcomes: 1) Di—OR = 0.63; 2) Cu—IRR = 0.85; 3) Co—f2 = 0.01.

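### The only stated route into moderator testing (section 8.1) is a significant factor-outcome association, which Secondary Aim 1 does not need and which can screen out true moderators

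*Combined protocol and SAP*

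**What the plan says.** Secondary Aim 1 (section 1.2.1) sets out to examine structural factors (housing, food, education, healthcare access) and individual-level factors (homophobia, stigma, discrimination): "factors as moderators of intervention outcomes". The aim itself carries no screening condition.

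Section 8.1 says that diagnostic, psychosocial, barrier/facilitator and sociodemographic variables "will be tested for significant association with study outcomes". Housing insecurity is one of its examples. The rule then reads: "All variables demonstrating significant statistical association with one or more of the study outcomes will be included as statistical covariates" in the multivariate analyses for Aims 1a to 1c, "and will additionally be included in exploratory sub-group analyses to test for moderating effects on treatment response". Both halves of that sentence have the same subject, the variables that passed the screen.

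Two other places bear on the point:

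- Table 2, in the row for the Admissions & Follow-up Form, lists "Barrier/Facilitator Moderator Analyses" with no model and no entry rule.
- Section 9 gives analyses for Aims 1a, 1b and 1c and none for Secondary Aim 1. Under Aim 1b (the first of two sections numbered 9.2) it says that the pooled pre/post model "provides increased analytical power for HIV subgroup and/or contingency analyses".

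**The concern.** A main association and a moderating effect are different quantities. A screen on the first selects factors that predict outcome, whereas the aim asks which factors change the effect of the app. Suppose men with a barrier do worse without the app but gain more from it. The two tendencies offset each other when the arms are combined, and the factor may not reach significance in the screen although it is the kind of factor the aim is looking for. A factor that is merely prognostic passes easily.

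At stake is the reading of Secondary Aim 1. A factor missing from the list of moderators might have been tested and found unimportant, or might never have been tested, and a report that follows section 8.1 need not make clear which. The estimates for Aims 1a to 1c do not depend on this half of the rule.

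**Working it through.** **Inputs from the plan.** "300 participants (n=150: Immediate Delivery / n=150: Delayed Delivery" (Schema); 80% methamphetamine use in the DD arm before access (section 8.2); minimum detectable OR 0.48 for dichotomous use in Aim 1a (section 9.1); "1 - β = 0.80; α = 0.05, two-tailed" (Table 2).

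**Assumptions.** Factor present in half the men, so 75 per arm-by-factor cell; screen at two-sided 0.05 (its level is not stated); screen on the month-1 outcome with arms combined (also not stated).

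**1. The plan's own figure.** Odds 4 × 0.48 = 1.92, so the rate in the ID arm is 1.92/2.92 = 65.8%. At 150 per arm the mean rate is 0.7288. The null SE is √(2 × 0.7288 × 0.2712/150) = 0.0513 and the alternative SE is √((0.1600 + 0.2252)/150) = 0.0507. Power = Φ((0.1425 − 1.96 × 0.0513)/0.0507) = 79.6%, so OR 0.48 reproduces. The plan gives no corresponding figure for any interaction.

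**2. Formulas.** The interaction is the difference between the two log odds ratios. Its SE is √Σ 1/(75·p(1−p)) over the four cells, and its power is Φ(|estimate|/SE − 1.96). The screen compares the pooled rates of the two factor groups, 150 men each.

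**3. Moderator with no main association.** Month-1 use in DD is 84% with the barrier and 76% without; in ID it is 62% and 70%.

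- Log ratio of ORs = (logit 0.62 − logit 0.84) − (logit 0.70 − logit 0.76) = −1.169 + 0.305 = −0.863, a ratio of 0.42.
- SE = √(0.0992 + 0.0566 + 0.0731 + 0.0635) = 0.541; power 36% by formula, 35% by simulation.
- Pooled use is (84 + 62)/2 = (76 + 70)/2 = 73% in both groups, so the screen is passed only at its false-positive rate of 5%.
- Passing and then detecting: about 0.05 × 0.36 = 0.018; simulation gives 1.5 to 1.6%.

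If any of three independent outcomes may admit the factor, the chance of entry is 1 − 0.95³ = 14%, still by chance alone.

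**4. Moderators that create a main association.** DD use is 80% in both factor groups, and the app works in one group only.

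| App OR in the two groups | ID use | Interaction SE | Direct power | Pooled rates screened | Screen passed | Passed and detected |
|---|---|---|---|---|---|---|
| 0.48 v 1.0 | 65.8% v 80% | 0.556 | 26% | 72.9% v 80% | 31% | 8% |
| 0.23 v 1.0 | 47.9% v 80% | 0.551 | 76% | 64.0% v 80% | 88% | 67% |

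The last column agrees with simulation and with the simple products 0.31 × 0.26 = 0.08 and 0.88 × 0.76 = 0.67.

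**5. Sensitivity to the time point.** Take the case in step 3 and let the effect persist. At baseline nobody is treated, and 84% v 76% passes the screen 41% of the time. At months 3, 6 and 9 everyone has had access, and 62% v 70% passes about 31% of the time at each. If significance at any of the five common time points admits the factor, and these are treated as independent, the chance of entry is 1 − 0.59 × 0.69³ × 0.95, about 81%. Detection at month 1 then falls from 35% to about 0.81 × 0.35 = 28%.

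**The case against.** The strongest case is textual. Section 8.1 states who is included. It does not state that all others are excluded, and the word 'only' does not appear. Secondary Aim 1 and the Table 2 entry both name moderation without a screen, so barriers and facilitators could be meant to receive moderator analyses in any event, with section 8.1 adding further exploratory sub-groups. This stands in part. A reader might infer that the plan definitely drops every factor that fails the screen, and the documents do not say so. But Table 2 names a destination and supplies neither entry rule nor model, while section 8.1 explicitly puts barriers through the screen. That leaves the screen as the only stated route.

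The second objection concerns size. The fall to about 2% needs exact cancellation and a pooled-arm month-1 screen. Steps 4 and 5 show much milder losses, so a general claim of near-total loss is not supported.

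Third, a reader might infer that the plan replaces an arm interaction with pooled pre/post sub-groups. Section 9.2 on Aim 1b speaks of HIV subgroup and contingency analyses and does not assign the 1.2.1 factors to them. Section 8.1 does not say how moderation will be tested, and an interaction term would fit its wording.

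Finally, the direct test has only 36% power in the step 3 case and the analyses are labelled exploratory. A null result would therefore be weak evidence even without the screen. That is a reason to report estimates and intervals for all named factors; it does not justify choosing them on prognosis.

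**Conclusion.** The point holds as a mismatch between rule and aim. The one stated entry condition for moderator testing is a main association, whereas Secondary Aim 1 concerns interaction. As written, the rule can leave out true moderators and favour prognostic factors.

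The size cannot be fixed from the documents. It ranges from near-total loss for a factor with no main association to a modest loss when the interaction itself produces a strong one, and it shrinks further if several time points count. All these figures rest on the assumed prevalence, screen level and interaction sizes. The change should be made, but it affects a secondary, exploratory aim and leaves the Aim 1a to 1c estimates untouched.

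**What to change.** For Secondary Aim 1, remove the main-association screen. List the structural and individual-level factors of section 1.2.1 in the SAP, using baseline values. Section 6.6.2.3 shows that housing, food security, education and stigma/discrimination are already collected at baseline. Healthcare access is not named there, so the item that measures it should be identified.

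Test each factor-by-randomised-arm interaction at month 1 in the planned mixed GLM, while the DD arm is still the randomised control. Report every interaction estimate with its confidence interval, label the set exploratory and note the limited power. State that moderation will not be inferred from separate sub-group p-values or from sub-group pre/post changes in the pooled sample. Make the Table 2 entry refer to this analysis.

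The cost is SAP wording and a few extra models. The downside is a slightly longer, fixed list of exploratory tests.
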